3.2 Efficacy outcome variables

3.2.1 Exacerbation

3.2.1.1 Annual exacerbation rate

The analysis is based on exacerbation events reported by the investigator in the eCRF. The exacerbation events will be categorised according to their onset date into on-study, on-treatment and post-treatment periods following the same algorithms used to classify study periods for AEs in Section 3.1.1 above. Similarly, for the analysis of adolescent data at Week 56 visit, only on-treatment exacerbations will be included in the adult completion analysis phase.

For the production of summary statistics, the annual exacerbation rate in each treatment group will be calculated for on-treatment, post-treatment and on-study periods using the time-based approach.

- Annual Exacerbation Rate (on-treatment)=Total number of on-treatment exacerbations *365.25/Total duration of on-treatment follow-up within the treatment group (days)
- Annual Exacerbation Rate (post-treatment)=Total number of post-treatment exacerbations *365.25/Total duration of post-treatment follow-up within the treatment group (days)
- Annual Exacerbation Rate (on-study)=Total number of on-study exacerbations *365.25/Total duration of on-study follow-up within the treatment group (days)

Where the durations of follow-ups for on-treatment, post-treatment and on-study periods will follow the definitions of corresponding study periods in the AE Section 3.1.1.

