4.1.1 Adult completion analysis

This analysis will be conducted when all adult patients within BORA have completed the study, and the final adolescent patient has completed the first 56 weeks of treatment within BORA. At this time, all of the study objectives related to adults will be fully addressed. The CSR will be prepared for the adult completion analysis as detailed below.

Data cutoff for this analysis will be the date when all adult patients within BORA have completed the study, and the final adolescent patient has completed the first 56 weeks of treatment within BORA. The analysis summary tables and figures will include adult data up to and including follow-up visit and adolescent data up to Week 56 visit or IPD visit, whichever is earlier, while all listings will include all adult data up to and including follow-up visit and adolescent data up to the date of data cut-off (therefore may include adolescent data beyond Week 56 that is not included in any analyses).

Summaries will be presented for patients enrolled from studies D3250C00017 and D3250C00018, separately for patients from study D3250C00020. Adult patients and adolescents will be separately summarised as well as combined.

For the analysis of adolescent data in the adult completion analysis, only on-treatment evaluations will be included in the summaries. For example, for summaries of AEs, only on-treatment AEs will be summarised for adolescents.

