4.2.5.1 Adverse events

Adverse events (AEs) will be summarised separately by the treatment group for the on-study, on-treatment and post-treatment periods, as defined in Section 3.1.1.

An overall summary table will be produced showing the number and percentage of patients with at least 1 AE in any of the following categories; AEs, serious adverse events (SAEs), deaths due to AE, and AEs causing discontinuation of the investigational product (DAEs). This summary will also be repeated by baseline blood eosinophil count ($<300/\mu\text{L}$, $\geq 300/\mu\text{L}$) for the on-study and on-treatment periods. The total number of AEs in the different AE categories in terms of AE counts will also be presented (ie, accounting for multiple occurrences of the same event in a patient).

AEs will be summarised by System Organ Class (SOC) and Preferred Term (PT) assigned to the event by MedDRA. For each PT, the number and percentage of patients reporting at least one occurrence will be presented, ie, for a patient multiple occurrences of an AE will only be counted once.

A summary of the most common (frequency of $\geq 5\%$ in any treatment group) AEs will be presented by PT. AEs (by PT) will be summarised by causality and maximum intensity. If a patient reports multiple occurrences of the same AE, the maximum intensity will be taken as the highest recorded maximum intensity (the order being mild, moderate, and severe). SAEs, DAEs, and deaths will also be summarised in separate tables.

Furthermore, events of interests such as injection site adverse events, hypersensitivity adverse events, adjudicated MACE+, and malignancies will be summarised separately.

The rate of AEs per person-years at risk, calculated as (number of patients reporting AE)/(total period with patients at risk of AE), will be reported for the on-study, post-treatment and on-treatment periods. The total period at risk for each patient within each study period will follow the definitions specified in Sections 3.1.1. Rates will typically be expressed in terms of events per 100 patient-years.

Separate listings of patients with AEs, SAEs, death due to AE, discontinuations due to AEs, as well as events of interest will be presented.

For the patients who rolled over to MELTEMI study, selective AE and SAE tables during study period will be summarised by treatment group. A listing of adjudicated MACE+ and malignancies will be also provided.

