8.2 Appendix B Partial and missing date imputation

Dates missing the day or both the day and month of the year will adhere to the following conventions in order to classify on-treatment AEs and to classify prior/concomitant medications.

For AE start date or medication start date:

Partial missing start date:

- Missing day of the month: 1st day of the month
- Missing day and month: Jan. 1st of the year

Completely missing start date:

- If AE end date or medication end date is missing, then impute the start date as the first visit date (Visit 1)
- If AE end date or medication end date is before the first visit date (Visit 1), then impute the start date as the end date
- If AE end date or medication end date is after the first visit date (Visit 1), then impute the start date as the first visit date (Visit 1)
- Otherwise, impute the start date as the first visit date (Visit 1)

For AE end date or medication end date:

Partial missing end date:

- Missing day of the month: Last day of the month
- Missing day and month: Dec. 31st of the year
- Further adjust by selecting the earlier of the imputed date, death date, and post-treatment end date*.

Post-treatment end date* is defined as the last visit date or the discontinuation of study day, whichever is later.

Completely missing end date:

- AE end date will be left as missing
- Medication end date will be imputed as earlier of death date and post-treatment end date (as defined above).

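### The AE rate puts patients over whole-period person-time but is labelled as events per 100 patient-years, so for very common AE categories an unchanged risk would look higher after treatment than on it

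*SAP*

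**What the plan says.** SAP Section 4.2.5.1 builds the rate in three steps.

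- Formula: "calculated as (number of patients reporting AE)/(total period with patients at risk of AE"). It "will be reported for the on-study, post-treatment and on-treatment periods".
- Time at risk: "The total period at risk for each patient within each study period will follow the definitions specified in Sections 3.1.1".
- Units: "Rates will typically be expressed in terms of events per 100 patient-years".

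The periods in SAP Section 3.1.1 are bounded by first dose, the EOT or IPD visit, last dose plus 28 or 35 days, and the follow-up visit. An AE does not end any of them.

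For exacerbations in the same three periods, SAP Section 3.2.1.1 uses events over follow-up time, for example "Total number of post-treatment exacerbations *365.25/Total duration of post-treatment follow-up within the treatment group (days"). Section 3.4 calculates health care encounter rates in a similar way. For AEs, Section 4.2.5.1 plans event totals ("The total number of AEs in the different AE categories in terms of AE counts will also be presented") but no person-time rate based on them.

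**The concern.** A patient-based numerator needs time that stops at the first event; an event-based label needs all events in the numerator. The SAP pairs a patient count with whole-period time and gives the result the event label, so it matches neither definition.

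The label is wrong at any incidence. The numerical consequence depends on how common the AE category is. Once a patient has had an AE, later time still adds to the denominator, but later AEs add nothing to the numerator. The longer the period, the lower the rate, even if the risk is constant. A person-time rate is meant to remove the effect of unequal follow-up; this one leaves part of it in.

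The primary objective covers both the treatment and the follow-up period, and those differ in length by a factor of almost five in adults. For any AE, or a large SOC, an unchanged risk would look like a rise after stopping, a real fall could be hidden, and the on-study rate would lie below both of its parts.

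**Working it through.** The plan states no AE rate or expected incidence, so there is no figure to reproduce. The check asks what the formula returns when the risk does not change.

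**Inputs.** The protocol synopsis (Duration of treatment) puts EOT at Week 56 and follow-up at Week 68 for adults. Period lengths in years (weeks × 7 / 365.25):

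- on-treatment, 56 weeks: 392 / 365.25 = 1.073
- post-treatment, 12 weeks: 84 / 365.25 = 0.230
- on-study, 68 weeks: 476 / 365.25 = 1.303

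The 56-week incidence *p* is assumed, from 5% to 70%.

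**Formulas.** Constant hazard λ = −ln(1 − *p*) / 1.073. Planned rate for a period of length *T*: 100 × (1 − exp(−λ*T*)) / *T*.

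**Example, *p* = 50%.** λ = 0.693 / 1.073 = 0.646 per year.

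- On-treatment: 0.50 / 1.073 = 46.6 per 100 patient-years.
- Post-treatment: (1 − exp(−0.1485)) / 0.230 = 0.138 / 0.230 = 60.0.
- On-study: (1 − exp(−0.8417)) / 1.303 = 0.569 / 1.303 = 43.7.

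**Results, per 100 patient-years:**

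| Assumed 56-week incidence | Constant rate (100λ) | Planned, on-treatment | Planned, post-treatment | Planned, on-study | Post / on |
|---|---|---|---|---|---|
| 5% | 4.78 | 4.66 | 4.75 | 4.63 | 1.02 |
| 10% | 9.82 | 9.32 | 9.71 | 9.22 | 1.04 |
| 30% | 33.2 | 28.0 | 32.0 | 27.0 | 1.14 |
| 50% | 64.6 | 46.6 | 60.0 | 43.7 | 1.29 |
| 70% | 112.2 | 65.2 | 98.9 | 58.9 | 1.52 |

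The planned rate also has a ceiling of 100 / *T*: 93.2 on treatment and 434.8 after it.

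**Masking.** The two planned rates are equal if the hazard after treatment is *r*λ with 1 − exp(−*r*λ × 0.230) = *p* × 12/56. At 50% the right side is 0.107, so *r* = 0.1133 / 0.1485 = 0.763, a 24% fall. At 70% it is 0.150, so *r* = 0.1625 / 0.2580 = 0.630, a 37% fall. Falls of that size would appear as no change.

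**Sensitivity to equal risk across patients.** With gamma frailty of variance 1, survival is 1 / (1 + λ*t*). Holding *p* at 50%, λ × 1.073 = 1, so the 12-week incidence is 0.2143 / 1.2143 = 0.1765 and the ratio is (0.1765 / 0.50) × (56 / 12) = 1.65. At 70% it is (0.3333 / 0.70) × (56 / 12) = 2.22. Variation between patients widens the gap.

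**Check by simulation.** With 1,200 patients, Poisson events, 70% incidence and 2,000 runs, the planned formula gave 65.2, 99.0 and 59.0 (on-treatment, post-treatment, on-study). Total AEs over person-time gave 112.2, 112.4 and 112.2. In a separate run of 1,000,000 patients at 75% incidence, the planned formula gave 69.9 on treatment and 111.7 after it, events over person-time gave 129.2 and 129.2, and patients over time to first AE gave 129.2 and 129.0. Both corrected forms stay level when the risk does.

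**The case against.** **Time at risk may already mean time to first AE.** A patient counted once could be regarded as no longer at risk, and Section 3.2.1.1 uses different words for whole-period follow-up. But the sentence after the formula sends the programmer to Section 3.1.1, whose periods do not stop at an AE. If time to first AE was intended, the SAP needs to say so, and the label would still be wrong.

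**No on- versus post-treatment AE comparison is planned.** This is right. The three periods are summarised separately, and the SAP amendment history gives the aim of seeing a change on withdrawal only for exacerbations and health care encounters. Even so, the same rate is reported for all three periods, and readers can be expected to compare them.

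**AEs may be captured less completely after Week 56.** Adults are seen every 4 weeks on treatment and then only at Week 68, and AEs are partly elicited by asking about the time since the last visit. Lower capture would pull the post-treatment rate down and could offset the artefact. The documents do not give the size of any such effect. It makes the direction of the observed figures less certain, but it does not make the formula correct.

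**The material effect is narrow.** This stands. It needs very common categories, and Section 4.2.5.1 already gives patient numbers, percentages and total AE counts for the overall categories. No test or decision rule uses the rate, and regimens with similar follow-up are affected alike.

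**An event rate answers a different question.** True: it gives more weight to patients with many recurrences. That is a reason to offer a properly defined patient-based rate as the alternative, not to keep the present mixture.

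**Conclusion.** The concern holds. As written, the AE rate counts patients, uses whole-period time and is labelled as events. With a constant risk, adults would show a post-treatment rate 29% above the on-treatment rate at an assumed 50% incidence and 52% above it at 70%. At 5% to 10% incidence the excess is 2% to 4% and the on-treatment rate is understated by about 2.5% to 5%. For rare events such as MACE+ and malignancy the effect is negligible.

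These sizes rest on assumed incidences, completed 56- and 12-week periods, a constant hazard and equal AE capture in both periods. In the main CSR, Section 4.1.1 limits summaries to "adolescent data up to Week 56 visit or IPD visit, whichever is earlier", so a further adult-versus-adolescent distortion arises only if the 108-week addendum is read beside the adult results.

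This should be fixed, because the rate describes the primary safety objective. It does not threaten the patient percentages, the AE counts or the comparison of regimens within a period.

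**What to change.** For anything labelled events per 100 patient-years, define the rate as the total number of AEs in the period divided by total person-time in the period, times 100, in line with Section 3.2.1.1. The cost is low: AE counts by category are already planned and the period lengths are already needed, so it takes one SAP sentence and a change of numerator. Its downside is the weight it gives to patients with many recurrences.

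If a patient-based rate is kept, label it as patients with an AE per 100 patient-years and stop each patient's time at the first onset of that category in the period. This costs more. It needs a separate denominator for each term and a rule for imputed onset dates: Appendix B sets "Missing day of the month: 1st day of the month" and usually moves a completely missing start date to Visit 1, which would shorten time at risk.

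State in each table which rate is shown. With either change, figures for common AE categories will be higher than under the present formula.

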4.2.5.2 Laboratory data

All continuous laboratory parameters will be summarised descriptively by absolute value at each visit by treatment group, together with the corresponding changes from baseline. All parameters will be summarised in SI units, with the exception of blood eosinophil counts which will be summarised in both SI and conventional units. Results which are reported from the central laboratory in conventional units will be converted to SI units for reporting.

Central laboratory reference ranges will be used for the identification of abnormalities, and a shift table will be produced for each laboratory parameter to display low, normal, high, and missing values. The shift tables will present baseline and maximum/minimum post-baseline value, as applicable for each parameter,

Shift plots showing each individual patient's laboratory value at baseline and at maximum/minimum post-baseline will be produced for each continuous laboratory variable. If any laboratory variables show any unusual features (high or low values or a general shift in the data points) at other time points then shift plots of these data may be produced.

Data for patients who have treatment-emergent values outside central laboratory reference ranges will be presented. This data presentation will include all visits for this subset of patients.

Maximum post-baseline bilirubin elevations by maximum post-baseline ALT and AST will be presented, expressed as multiples of ULN. Bilirubin will be presented in multiples of the

following ULN ≤ 1.5 , $>1.5-2$, >2 , and AST and ALT will be presented in multiples of the following ULN ≤ 1 , $>1-3$, $>3-5$, $>5-10$, >10 .

Maximum post-baseline total bilirubin will be presented (<2 and ≥ 2 x ULN) and plotted against maximum post-baseline ALT (<3 , $\geq 3 - <5$, $\geq 5 - <10$, and ≥ 10 x ULN), expressed as multiples of ULN. This will be repeated to show maximum post-baseline total bilirubin against maximum post-baseline AST.

Data for patients with ALT or AST ≥ 3 x ULN, and bilirubin ≥ 2 x ULN will be presented, which will include all visits for this subset of patients. A line plot of liver biochemistry test results (including ALP, ALT, AST, total bilirubin, and GGT) over time will also be presented for this subset of patients.

A summary of shifts from baseline to maximum post-baseline Common Terminology Criteria for Adverse Events (CTCAE) grade will be produced for white blood cell counts and its components using CTCAE version 4.03 (June 14, 2010). The summary of shifts from baseline to maximum grade post-baseline will be produced, with results categorised as no grade, grades 1 to 4. White blood cells included in these summaries are: CD4 + T-cells, neutrophils, lymphocytes, and leukocytes. These will be from the CBC reports and will be done by absolute count. B-cells, CD4 + T-cells, CD8 + T-cells, NK cells are measured by flow cytometry. The cell counts by flow cytometry will also be summarised by shifts tables (categorised for the minimum value as low, normal, and high), based on both percentage cells and absolute cell counts.

For urinalysis data, a shift table will be generated to present changes from baseline to maximum post-baseline value for each parameter and will include patients with both baseline and post-baseline data.

Descriptive statistics and change from baseline at each visit will be presented for IgE by treatment group for adolescent patients.

Any data outside the central laboratory normal reference ranges will be explicitly noted on the listings that are produced.

For the patients who rolled over to MELTEMI study, the following safety lab tables will be presented by treatment group:

- Data for patients who have treatment-emergent values outside central laboratory reference ranges
- Data for patients with ALT or AST ≥ 3 x ULN, and bilirubin ≥ 2 x ULN

4.2.5.3 Physical examination

Shift tables (normal, abnormal) of baseline versus EOT will be generated, presenting the assessment for each component of the complete physical examination separately.

Listings of abnormal results will be produced.

4.2.5.4 Electrocardiographs

The Investigator's assessment of the 12-lead ECG (normal or abnormal) will be listed for all patients, along with detailing whether any abnormalities were clinically significant or not.

A shift table will be generated to display normal, abnormal – not clinically significant, abnormal – clinically significant, and not done. The table will be presented for baseline and the last post baseline observation.

4.2.5.5 Vital signs

Descriptive statistics and change from baseline for vital signs data will be presented for each treatment group by visit. Baseline to maximum post-baseline and baseline to minimum post-baseline value shift tables will be generated, as applicable for each parameter and will include patients with both baseline and post-baseline data. All recorded vital signs data will be listed.

4.2.6 Analysis methods for efficacy variables

All efficacy data from SIROCCO and CALIMA will be summarized by treatment for the patients with predecessor baseline blood eosinophil count $\geq 300/\mu\text{L}$ and $< 300/\mu\text{L}$. Efficacy data from ZONDA will be summarised for the FAS regardless of predecessor baseline eosinophil counts.

4.2.6.1 Asthma exacerbation

Annual asthma exacerbation rate

The annual asthma exacerbation rate will be summarised descriptively by the treatment group. On-treatment exacerbation, post-treatment exacerbation, as well as on-study exacerbation rates will be summarised separately. All exacerbation incidences will be listed.

Time to the first asthma exacerbation

Time to the first asthma exacerbation will be described using a Kaplan-Meier plot by the treatment group. Note that this calculation will only be displayed for patients who received placebo in the predecessor studies.

4.2.6.2 Pre- and post-bronchodilator FEV₁ measured at the study centre

Summary statistics of the change from baseline in the pre- and post-bronchodilator FEV₁ will be produced for all post-baseline visits by treatment group.

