
 1. To assess the effect of 2 dosing regimens of benralizumab on asthma related and general health-related quality of life for adult patients during the 56-week treatment period and through the follow-up period (16 weeks from day of last dose) 2. To assess the effect of 2 dosing regimens of benralizumab on asthma related and general health-related quality of life for adolescent patients during the 108-week treatment period and through the follow-up period (16 weeks from day of last dose) 	
 • AQLQ(S)+12 • EQ-5D-5L

 1. To assess the effect two dosing regimens of benralizumab on asthma control for adult patients during the 56-week treatment period and through the follow-up period (16 weeks from day of last dose) 2. To assess the effect two dosing regimens of benralizumab on asthma control for adolescent patients during the 108-week treatment period and through the follow-up period (16 weeks from day of last dose) 	
 • ACQ-6

 1. To evaluate the pharmacokinetics and immunogenicity of 2 dosing regimens of benralizumab for adult patients during the 56-week treatment period and through the follow-up period (16 weeks from day of last dose) 2. To evaluate the pharmacokinetics and immunogenicity of 2 dosing regimens of benralizumab for adolescent patients during the 108-week treatment period and through the follow-up period (16 weeks from day of last dose) 	
 • PK parameters • Anti-drug antibodies (ADA)

Objective	Endpoint

 1. To assess the effect of 2 dosing regimens of benralizumab on pulmonary function for adult patients during the 56-week treatment period and through the follow-up period (16 weeks from day of last dose) 2. To assess the effect of 2 dosing regimens of benralizumab on pulmonary function for adolescent patients during the 108-week treatment period and through the follow-up period (16 weeks from day of last dose) 	
 • Pre-bronchodilator FEV₁ and post-bronchodilator FEV₁ at the study center

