4.2.3.3 Adolescents within the European Union

Adolescents previously assigned to an active treatment arm in the predecessor study

Adolescents within the European Union (EU) will continue to receive only the Q8W dosing regimen as per the predecessor study. In order to maintain the blind of the predecessor study, this group will receive the injections every 4 weeks for the first 3 doses (active drug at Visits 1 and 3, placebo administered at Visit 2) followed by every 8 weeks thereafter (to match the regimen of the adolescents who were on placebo in the predecessor study).

Adolescents within the EU will thereafter be receiving open label treatment. These adolescent patients will follow an every 4 weeks Study Visit schedule; however, investigational product (IP) will only be administered at every other visit after the first 3 doses as described above.

Adolescents previously assigned to the placebo arm in the predecessor study

Adolescents within the EU who were randomized to placebo in the predecessor study will be assigned to benralizumab 30 mg every 8 weeks in this safety extension study (every 4 weeks for the first 3 doses followed by every 8 weeks thereafter).

After the first 3 doses, adolescent patients within the EU will be receiving open label treatment with IP administered at their bimonthly visit.

With no placebo arm in this safety extension study, adolescent patients within the EU will thus be receiving open label treatment. These adolescent patients will follow an every 4 weeks Study Visit schedule; however, IP will only be administered at every other visit after the first 3 doses as described above.

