Spirometry testing should be done according to the schedule provided in Table 1 or Table 2. All spirometry assessments should be performed within ± 1.5 hours of the time that the first spirometry in the study (Visit 1) was performed. For example, if the first spirometry was started at 8:00 AM, then all subsequent spirometry testing should be initiated between 6:30 AM and 9:30 AM. Ideally, these assessments should be conducted at the same time of day as in the predecessor study, wherever possible.

Spirometry technique

Patients should avoid engaging in strenuous exertion for at least 30 minutes prior to spirometry measurements. Patients should avoid eating a large meal for at least 2 hours prior to spirometry

measurements at the center. Forced expiratory maneuvers should be performed with the patient seated in an upright position. If this is not comfortable for the patient, standing is permitted. The same position should be used by the patient for each forced expiratory maneuver from enrolment throughout the study. The head must not be tilted during maneuvers and the thorax should be able to move freely; hence tight clothing should be loosened. A nose-clip should be used for the maneuver. Disposable mouthpieces of the same dimension and shape should be used as far as possible for the duration of the study.

The forced expiratory maneuver (FEV₁ and FVC) should start with a maximal inspiration and then followed by a fast and forceful expiration that should last for at least 6 seconds. It is important to encourage the patient to continue the expiration to be fast and forceful throughout the maneuver. Ensure that none of the following has occurred: coughing during the first second, glottis closure, leak or obstruction of the mouthpiece (by the tongue).

Multiple forced expiratory efforts (at least 3 but no more than 8) will be performed for each center spirometry session and the 2 best efforts that meet the ATS/ERS acceptability and reproducibility criteria will be recorded. The best efforts will be based on the highest FEV₁. The absolute measurement (for FEV₁ and FVC), and the percentage of predicted normal value (Quanjer et al 2012) will be recorded. The highest FVC will also be reported regardless of the effort in which it occurred (even if the effort did not result in the highest FEV₁).

Post-bronchodilator spirometry

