Post-BD spirometry will be performed as an efficacy measure on designated center visits during the treatment period as listed in Table 1 and Table 2.

Order of administration of usual asthma controller medication and IP relative to scheduled pre- and post-bronchodilator spirograms

The patient's usual morning asthma controller therapy must not be given until after the initial pre-medication, pre-bronchodilator spirograms are complete for the reasons discussed above; usual asthma controller may be given after final post-bronchodilator spirograms.

Record keeping

A signed and dated copy of the pre- and post- BD printout must be kept at study center for source data verification. The printout must be marked with the study code, enrolment code, date and time of measurement, and visit number.

Spirometry references

The Global Lung Function Initiative (GLI) equations will be used to determine the patient's predicted normal (PN) values (Quanjer et al 2012).

[figure not shown]
FEV₁ expressed as percent of the PN value will be calculated as follows:

$$\text{FEV}_1\% \text{ of PN} = \text{FEV}_1 \text{ measured} / \text{FEV}_{1\text{PN}} \times 100$$

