8.4.1.3 Forced expiratory volume in 1 second

The change from baseline to each of the post-randomization visits (post Visit 1 up to and including the EOT visit) will be used as secondary efficacy variables.

The last measurement recorded prior to the first dose (Visit 1) will be used as baseline FEV₁.

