3.2.2 Lung function

The absolute and the changes from baseline to each of the post-baseline visits as scheduled in Table 1 (adults) and Tables 2A and 2B (adolescents) of the CSP on pre-BD FEV₁ and post-BD FEV₁ will both be summarised.

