| Week 0 | 1 | Study Day \leq 1 |
| Week 12 | 85 | 2 \leq Study Days \leq 238 |
| Week 56 (EOT for adults) | 393 | 239 \leq Study Days \leq 574 |
| Week 108* (EOT for adolescents) | 757 | 575 \leq Study Days |

For chemistry labs: Calcium, Chloride, CO₂, Glucose, Phosphorus, Potassium, Sodium, Total cholesterol and Uric acid.

* Visits for adolescents only.

Table 7 Adjusted visit windows for PK (unscheduled samples only) and ADA (including nAb)

| Analysis Visit | Scheduled study day | Adjusted visit window |
|---------------------------------|----------------------------|----------------------------------|
| Week 0 | 1 | Study Day \leq 1 |
| Week 8 | 57 | 2 \leq Study Days \leq 84 |
| Week 16 | 113 | 85 \leq Study Days \leq 154 |
| Week 28 | 197 | 155 \leq Study Days \leq 252 |
| Week 44 | 309 | 253 \leq Study Days \leq 336 |
| Week 52 | 365 | 337 \leq Study Days \leq 385 |
| Week 56# (EOT for adults) | 393 | 386 \leq Study Days \leq 434 |
| Week 68# (FU for adults) | 477 | 435 \leq Study Days |
| Week 60* | 421 | 386 \leq Study Days \leq 476 |
| Week 76* | 533 | 477 \leq Study Days \leq 588 |
| Week 92* | 645 | 589 \leq Study Days \leq 700 |
| Week 108* (EOT for adolescents) | 757 | 701 \leq Study Days \leq 798 |
| Week 120* (FU for adolescents) | 841 | 799 \leq Study Days |

Visit for adult only.

* Visits for adolescents only.

Note that the Week 52 window has a shorter window range (3 weeks) post scheduled study day due to adjustment for adult group having a scheduled EOT visit 4 weeks later.

Table 8 Adjusted visit windows for Pre-BD spirometry

| Analysis Visit | Scheduled study day | Adjusted visit window |
|---------------------------------|---------------------|----------------------------------|
| Week 0 | 1 | Study Day \leq 1 |
| Week 16 | 113 | 2 \leq Study Days \leq 168 |
| Week 32 | 225 | 169 \leq Study Days \leq 280 |
| Week 48 | 337 | 281 \leq Study Days \leq 385 |
| Week 56# (EOT for adults) | 393 | 386 \leq Study Days |
| Week 64* | 449 | 386 \leq Study Days \leq 504 |
| Week 80* | 561 | 505 \leq Study Days \leq 616 |
| Week 96* | 673 | 617 \leq Study Days \leq 728 |
| Week 108* (EOT for adolescents) | 757 | 729 \leq Study Days |

Visit for adult only.

* Visits for adolescents only.

Note that Week 48 window has shorter window range (7 weeks) post scheduled study day due to adjustment for adult group having a scheduled EOT visit 8 weeks later.

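### Adolescent FEV1 is summarised only on the raw scale over up to 108 weeks with no placebo or untreated arm, so growth is mixed with any drug effect, although percent-predicted FEV1 is already recorded

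*SAP*

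**What the plan says.** Protocol section 2 sets a secondary objective specific to this age group: "To assess the effect of 2 dosing regimens of benralizumab on pulmonary function for adolescent patients during the 108-week treatment period". The endpoint is pre- and post-bronchodilator FEV1 at the study center, and Protocol 8.5.1 lists change from baseline in both among the efficacy endpoints.

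SAP 3.2.2 defines the variables as "The absolute and the changes from baseline to each of the post-baseline visits", for pre- and post-bronchodilator FEV1. The method in SAP 4.2.6.2 is: "Summary statistics of the change from baseline in the pre- and post-bronchodilator FEV₁ will be produced for all post-baseline visits by treatment group". Neither section names a unit, percent of predicted or an adjustment for height, and SAP section 6 records no change from the protocol.

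The protocol collects more than this. Section 5.1.2 requires the absolute FEV1 and FVC "and the percentage of predicted normal value" to be recorded. It names the GLI equations as the reference and introduces the formula: "FEV₁ expressed as percent of the PN value will be calculated as follows". The adolescent schedules (Tables 2A and 2B) include repeated height measurements.

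On baseline, Protocol 8.4.1.3 says: "The last measurement recorded prior to the first dose (Visit 1) will be used as baseline FEV₁". On control, Protocol 4.2.3.3 begins a sentence "With no placebo arm in this safety extension study".

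**The concern.** Raw FEV1 rises as an adolescent grows. Without a placebo or untreated arm, change from baseline within a group is the main evidence on whether lung function improved, held or fell under benralizumab. On the raw scale, that change adds growth to whatever the drug does.

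The direction of the possible error depends on the predecessor arm:

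- **Predecessor placebo.** Baseline precedes the first active dose, so growth can look like a gain from starting treatment.
- **Predecessor active.** Baseline is already on treatment, so growth is more likely to hide a decline relative to the predicted value. In a safety extension this may be the more serious of the two.

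The adolescent completion analysis (SAP 4.1.2) is reported as its own addendum and is the analysis that reaches Week 108. It contains no adults in whom the drift would be absent.

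**Working it through.** The plan states no FEV1 effect, standard deviation or growth rate, so there is no planned figure to reproduce. The calculation below is an illustration under stated assumptions.

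**From the documents**

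- Age 12 to 17 at predecessor enrolment (SAP 4.1).
- Week 108 is study day 108 × 7 + 1 = 757, as in SAP Appendix A. Elapsed time is t = 756/365.25 = 2.07 years.
- Adolescent pre-bronchodilator analysis visits are Weeks 16, 32, 48, 64, 80, 96 and 108; Week 56 is marked adults only (SAP Table 8). For Week 48, t = 336/365.25 = 0.92 years.

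**Assumed (not in the documents)**

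- Starting FEV1 2.5 L; height h0 of 150 to 155 cm; growth g of 3 to 7 cm/year.
- FEV1 proportional to height to the power p, with p from 2.0 to 2.5.
- The predicted value rises with height and age.

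**Growth component with no drug effect:** 2.5 × [((h0 + g·t)/h0)^p − 1]

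- Week 108, low corner (155 cm, 3 cm/year, p = 2.0): 2.5 × (1.0401² − 1) = 0.20 L.
- Week 108, high corner (150 cm, 7 cm/year, p = 2.5): 2.5 × (1.0966^2.5 − 1) = 2.5 × 0.2593 = 0.65 L.
- Week 48, same corners: 0.09 and 0.28 L.
- Growth of 1 cm/year: 0.07 to 0.09 L by Week 108.
- No growth: 0 L.

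**Cross-check without a height model.** If FEV1 rises by 0, 0.05, 0.10, 0.20 or 0.30 L/year from growth, multiplying by 2.07 gives 0, 0.10, 0.21, 0.41 or 0.62 L by Week 108.

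**Masking a decline.** Take the low corner (155 cm, 3 cm/year, p = 2.0) and suppose the patient loses 5% relative to predicted. FEV1 at Week 108 is 2.5 × 1.0817 × 0.95 = 2.57 L. The raw table shows a gain of about 0.07 L; percent predicted shows the 5% relative loss.

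**What percent predicted does.** A patient who stays at 75% of predicted, while the predicted value rises by 0.05, 0.10, 0.20 or 0.30 L/year, gains 0.75 × rate × 2.07 = 0.08, 0.16, 0.31 or 0.47 L in raw FEV1 by Week 108. The change in percent predicted is 0 points throughout.

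**The case against.** Several points on the other side stand, and they limit the concern.

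- **Descriptive study.** In general no tests or p-values are planned, and the protocol endpoint is raw FEV1. That argues against removing raw FEV1, but not against adding a scale that separates growth.
- **Two concurrent regimens.** Predecessor-placebo adolescents outside the EU are randomised 1:1 to Q4W or Q8W, so growth should largely cancel in that comparison. It contrasts two active regimens, however, and does not show what either does to lung function. All EU adolescents go to Q8W (Protocol 6.5), and the treatment groups in SAP 4.1 do not separate them out.
- **Non-growers.** Some adolescents will have stopped growing. For them the growth component is zero.
- **Practicalities.** Height is measured at fewer visits than the full schedule and is not tied to each spirometry session. The documents do not say which height enters the predicted value.

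A reader might infer stronger claims that the documents do not support:

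- *That only change is reported.* SAP 3.2.2 also summarises absolute values, although raw absolute values carry growth too. Litres are an inference, since the SAP names no unit.
- *That growth will be read as a drug effect, or that the objective cannot be answered.* This is a risk whose size depends on growth data the documents lack.
- *That the combined adult and adolescent table carries the same distortion.* SAP 4.1.1 limits adolescent data in those tables to Week 56 or the IPD visit, and Table 8 places adolescents at Weeks 16, 32 and 48 in that period for pre-bronchodilator FEV1. They are also few: the SAP's amendment history calls them a small group, against about 1200 adults planned to remain in BORA.

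**Conclusion.** The point holds for adolescents. The SAP plans raw FEV1 and its change, and no post-baseline percent-predicted or height-adjusted summary, for patients who may still be growing and are followed to Week 108 without a placebo or untreated arm. Within-group change can therefore suggest benefit or conceal a relative decline.

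The size ranges from 0 L, where growth has stopped, to about 0.20 to 0.65 L by Week 108 for the assumed 2.5 L, 150 to 155 cm patient growing 3 to 7 cm/year. The upper range describes a short patient growing throughout, not the average adolescent in the study. The conclusion that the scales differ needs only that some adolescents are still growing; the litre figures rest entirely on the assumptions listed. The adult tables are unaffected, and the combined table only slightly.

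**What to change.** In SAP 3.2.2 and 4.2.6.2:

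1. Add value and change from baseline in percent-predicted FEV1 (GLI, pre- and post-bronchodilator) by visit and treatment group as the lead FEV1 summary for adolescents, in both the adult completion and adolescent completion analyses.
2. State the rule for the predicted value: age at the visit and the nearest measured height.
3. Keep raw FEV1 alongside for adolescents as supportive, since it is the protocol endpoint.
4. Leave the adult and combined raw FEV1 tables as planned. Footnote the combined table to say that it includes growing adolescents with data up to Week 56.

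The cost is one extra set of descriptive tables and the height rule. No new assessments are needed, because percent-predicted FEV1 and height are already collected.
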